## Figure 1 - Study Design Schematic

Fusion

**eClinical Suite** 

## Table 1 - Schedule of Events for Active Participants.

STUDY PROCEDURE	Study Day 1	Week 12	Week 24	Week 36	Week 48	Week 60	Week 72	Week 84	Week 96	Repeat Visit A e	Repeat Visit B f	End of Study / Early Term
Informed Consent	X											
Vital Signs	X b	X	X	X	X	X	X	X	X	X	X	X
Height & Weight	X b	X	X	X	X	X	X	X	X	X	X	X
Physical Examination	Xbe	*	*	*	Χ°	*	*	*	Χ°	*	Хс	X °
Chemistry, Hematology, Urinalysis	X b		X		X		X		X		X	X
ECG	X b		X		X		X		X		X	X
Drug Dispensation d	X	X	X	X	X	X	X	X	X	X	X	
Drug Accountability		X	X	X	X	X	X	X	X	X	X	X
Adverse Events	X b	X	X	X	X	X	X	X	X	X	X	X
Concomitant Medications	X b	X	X	X	X	X	X	X	X	X	X	X
C-SSRS – Since Last Visit	X b	X	X	X	X	X	X	X	X	X	X	X

\* Brief physical exam.

<sup>e Repeat Visit A occurs 12 weeks following the Week 96 visit and then reoccurs every 24 weeks thereafter. f Repeat Visit B occurs 12 weeks following the first Repeat Visit A and then reoccurs every 24 weeks thereafter.

<sup>a Study Day 1 will take place during the Month 24 Visit for study PTI-125-04.

<sup>b Data collected at Month 24 Visit for study PTI-125-04 will be used.

<sup>c Full physical examination at Day 1 (as part of Month 24 Visit from study PTI-125-04), Week 48, Week 96, and Repeat Visit B, and at End of Study or Early Term Visit.

<sup>d Drug will be dispensed at Study Day 1 and every 12 weeks.

## Table 2 – Schedule of Events for Re-entry Participants.

STUDY PROCEDURE	Re- entry Day 1	Re-entry Week 4 e	Repeat Visit	Repeat Visit	End of Study / Early Term
Informed Consent	X				
Medical History	X				
Inclusion/Exclusion Criteria	X				
Vital Signs	X	X	X	X	X
Height & Weight	X	X	X	X	X
Physical Examination	X a	*	*	Xª	X a
Chemistry, Hematology, Urinalysis	X	X		X	X
ECG	X	X		X	X
Drug Dispensation b	X		X	X	
Drug Accountability		X	X	X	X
Adverse Events	X	X	X	X	X
Concomitant Medications	X	X	X	X	X
C-SSRS – Since Last Visit	X	X	X	X	X

\* Brief physical exam.

a Full physical examination at Re-entry Day 1, Repeat Visit B, and at End of Study or Early Term Visit.

b Drug will be dispensed at Re-entry Day 1 and every 12 weeks thereafter.

c Repeat Visit A occurs 12 weeks following the Re-entry Day 1 visit and then reoccurs every 24 weeks thereafter.

d Repeat Visit B occurs 12 weeks following the first Repeat Visit A and then reoccurs every 24 weeks thereafter.

e Re-entry Week 4 visit only for subjects who completed the PTI-125-09 study >60 days prior to completing Re-entry Day 1.

## **Statistical Analysis Plan**

## 4.2. Inclusion-Exclusion Criteria and General Study Population

All subjects must comply with the following Inclusion Criteria:

- 1. Must have completed the PTI-125-04 study or Week 96 in the PTI-125-09 study.
- 2. Male subjects must be willing to continue use of contraception during the study. With female partners of childbearing potential, male subjects, regardless of their fertility status, must agree to either remain abstinent or use condoms in combination with one additional highly effective method of contraception (e.g., oral or implanted contraceptives, or intrauterine devices) or an effective method of contraception (e.g., diaphragms with spermicide or cervical sponges) during the study and for 14 days after study drug dosing has been completed.

Subjects meeting the following Exclusion Criterion will be excluded from the study:

1. Anything that in the opinion of the Investigator would preclude participation in this extension study. For anyone resuming study participation, any significant medical event or hospitalization during the gap period must be discussed with the medical monitor.

#### 5. SAMPLE SIZE

Up to 180 subjects may be enrolled in this study. Eligible subjects include those who completed PTI-125-04.

## 6. GENERAL ANALYSIS CONSIDERATIONS

## 6.1. Analysis Population

The Safety analysis set will include all patients who receive at least one dose of the study treatment. All safety analyses will be based on the Safety population.

## 6.2. Covariates and Subgroups

### 6.2.1. Planned Covariates

No covariates are planned for the analyses.

## 6.2.2. Planned Subgroups

No subgroups are planned for the analyses.

## **Statistical Analysis Plan**

## 6.3. Management of Analysis Data

## 6.3.1. Definition of Analysis Timepoints

Scheduled analysis visits are visits upon scheduled time points as specified in Table 1 - Schedule of Events for Active Participants and Table 2 – Schedule of Events for Re-entry Participants.

There will be no analyses performed based upon analysis timepoints.

## 6.3.2. Missing Data

### Partial or Missing Dates:

Missing data will not be imputed for the purpose of primary inference. All data recorded on the electronic case report form (eCRF) will be included in the safety data listings.

If complete Adverse Event (AE) start date is missing and AE end date is on or after the date of first dose, then the AE will be counted as a treatment emergent AE (TEAE) for the study.

If an AE has a partial missing start or stop date, the following rules will be used for imputation:

- If year is present but month and day are missing, impute start date as first dose date if the year is the same as the year of first dose date, otherwise January 1 of that year and impute stop date as last dose date if the year is the same, otherwise December 31 of that year.
- If year and day are present but month is missing, impute start month as first dose date
  month if AE start day greater than or equal to first dose day and if the year is the same,
  otherwise January and impute stop month as last dose date month if AE end day less than
  or equal to last dose day and if the year is the same, otherwise December of that year.
- If year and month are present but day is missing, impute start date as first dose day if the
  year and month are the same as the year and month of first dose date, otherwise first day
  of that month and impute stop date as last dose day if year and month are the same,
  otherwise last day of that month.

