### 8.1. Adverse Events

The Medical Dictionary for Regulatory Activities (MedDRA) dictionary (v27.0) will be used for coding AEs on the OLE Adverse Event eCRF.

Analyses of AEs will be performed for those events that are considered treatment emergent (TEAE), where treatment emergent is defined as any AE with onset or worsening on or after the First Study Dose in the OLE study and will be summarized for overall safety population.

The following summary tables will be presented:

- Overall Summary of TEAEs
- TEAEs by system organ class (SOC) and preferred term (PT)
- TEAEs by PT
- TEAEs by SOC, PT, and Maximum Severity
- TEAEs by SOC, PT, and Relationship to Study Drug
- Treatment Emergent Serious AEs (TESAEs) by SOC and PT

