## 9. TABLES AND LISTINGS

## Table 1: Data Summary Tables and Listings

Table Number	Table Title	Population		
14.1	Demographic Data			
14.1.1	Disposition			
	Summary of Subject Dispositions	Safety Analysis Population		
14.1.2	Demographics			
	Summary of Demographics and Baseline Characteristics	Safety Analysis Population		
14.3	Safety Data			
14.3.1	Displays of Adverse Events			
14.3.1.1	Summary of Treatment Emergent Adverse Event	Safety Analysis Population		
14.3.1.2	Summary of Treatment Emergent Adverse Event by System Organ Class and Preferred Term	Safety Analysis Population		
14.3.1.3	Summary of Treatment Emergent Adverse Event by Preferred Term	Safety Analysis Population		
14.3.1.4	Summary of Treatment Emergent Adverse Event by System Organ Class, Preferred Term and Maximum Severity	Safety Analysis Population		
14.3.1.5	Summary of Treatment Emergent Adverse Event by System Organ Class, Preferred Term and Relationship to Study Drug	Safety Analysis Population		
14.3.1.6	Summary of Treatment Emergent Serious Adverse Event by System Organ Class, Preferred Term	Safety Analysis Population		

14.3.1.7	Summary of Treatment Emergent Serious Adverse Event led to discontinuation of study by System Organ Class, Preferred Term	Safety Analysis Population	
Listing Number	Listing Title	Population	
16.2	Participant Data Listings		
16.2.1	Discontinued Subjects		
	Participant Disposition	Safety Analysis Population	
16.2.4	Demographic Data		
	Demographic and Baseline Characteristics	Safety Analysis Population	
16.2.7	Adverse Event Listing		
16.2.7.1	Listing of All TEAEs	Safety Analysis Population	
16.2.7.2	Listing of All TESAEs	Safety Analysis Population	
16.2.7.3	Listing of All TEAEs Leading to Study Discontinuation	Safety Analysis Population	
16.2.7.4	Listing of All TEAEs Leading to Deaths	Safety Analysis Population

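### SAP 6.3.2 leaves an ongoing AE with no start date without a treatment-emergent status, and its partial-date rules can turn an AE that ended before first dose into a TEAE

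*SAP*

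**What the plan says.** **Wholly missing start date (SAP 6.3.2).** The condition is "If complete Adverse Event (AE) start date is missing and AE end date is on or after the date of first dose". Where a record meets that condition, the stated consequence is "then the AE will be counted as a treatment emergent AE (TEAE) for the study". No branch follows for records that do not meet the condition.

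**Partial dates (SAP 6.3.2).** "If an AE has a partial missing start or stop date, the following rules will be used for imputation". Three bullets follow, and each needs the year to be known. With only the year known, the instruction is "impute start date as first dose date if the year is the same as the year of first dose date". With month and year known, the first-dose day is used when both match those of first dose. Neither bullet looks at the event's recorded stop date when it sets the start.

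**Definition and scope (SAP 8.1).** The definition reads "where treatment emergent is defined as any AE with onset or worsening on or after the First Study Dose in the OLE study". On scope, "Analyses of AEs will be performed for those events that are considered treatment emergent (TEAE".

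**Outputs (SAP 8.1 and 9).** Seven AE tables (14.3.1.1 to 14.3.1.7) and four AE listings (16.2.7.1 to 16.2.7.4) are planned. All are titled for treatment-emergent events or treatment-emergent serious events; the broadest listing is "Listing of All TEAEs".

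**Listing commitment.** SAP 6.3.2 also says "All data recorded on the electronic case report form (eCRF) will be included in the safety data listings", and 6.4.1 makes a similar promise for all data by subject.

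**Other missing AE attributes (SAP 6.3.2.1).** A missing relationship is taken as related, and a missing severity as severe.

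**The concern.** The objective is long-term safety, and the AE outputs are the only safety display. SAP 3.1 and 8.2 to 8.5 drop the summaries and listings of laboratory, vital-sign, physical-examination and ECG results; a finding appears only if the investigator judged it significant and it was recorded as an AE. Whether a record is flagged as treatment-emergent therefore decides whether it is reported.

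Two kinds of record are handled badly. An ongoing event of unknown onset has no route to treatment-emergent status through the date rules. This runs against the SAP's own cautious defaults for missing relationship and severity. An event known to have finished before first dose can be pulled in, with a start later than its stop. The first understates incidence and the second overstates it, so they cannot be described as one bias, and nothing suggests that they cancel.

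**Working it through.** The plan gives no figure to reproduce. The check is to run each date pattern through the rules of SAP 6.3.2. I take an illustrative first OLE dose of 15 Jun 2022; this date is an assumption, and only the order of dates matters.

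| Case | Start recorded | End recorded | Result under SAP 6.3.2 | Sensible? |
|---|---|---|---|---|
| A | none | 5 Jan 2023 | TEAE by the stated rule | yes |
| B | none | 1 Mar 2022 | rule not met; onset must precede first dose, so not a TEAE | yes |
| C | none | partial, year known | end date imputed, then as A or B | yes |
| D | none | none (ongoing) | no rule applies; status undefined | **gap** |
| E | 2022 | 10 Feb 2022 | start set to 15 Jun 2022; TEAE | **no** |
| F | Jun 2022 | 10 Jun 2022 | start set to 15 Jun 2022; TEAE | **no** |

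**Case D.** The partial-date bullets cannot help, because no part of the start date is known. The definition in 8.1 cannot be evaluated on a blank onset date; only a dated worsening could qualify the event. If the program tests whether the end date is on or after first dose, a blank end date fails. In SAS, the software named in SAP 6.3.5, a missing date compares as lower than any real date, so the record falls silently to not treatment-emergent.

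**Which outputs case D could touch.** There are 7 + 4 = 11 AE outputs. Protocol 9.5 requires an SAE entry to carry at least the term, start date and relationship, so a wholly missing start should not arise for an SAE reported as required. That largely protects four outputs: Tables 14.3.1.6 and 14.3.1.7, Listing 16.2.7.2, and Listing 16.2.7.4 (death is an SAE outcome under protocol 9.4). The other 11 − 4 = 7 are exposed, for non-serious events: Tables 14.3.1.1 to 14.3.1.5 and Listings 16.2.7.1 and 16.2.7.3.

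**Cases E and F.** The imputed start falls after the recorded stop by 125 days in E (10 Feb to 15 Jun) and by 5 days in F. Both events ended before first dose, so neither can have begun on or after it. Such records can exist: the schedule of events for active participants takes the Study Day 1 AE data from the parent study's Month 24 visit.

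**Scale per record.** Protocol 10.3 caps enrolment at 180. One subject is 1/180 = 0.56 percentage points. If 1 to 5 subjects were affected in the same table row (an assumption), the error is 1/180 = 0.56 to 5/180 = 2.8 points.

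**After the fix.** D becomes a TEAE; E and F become non-TEAEs; A, B and C are unchanged.

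**The case against.** A reader might infer that the SAP excludes ongoing events of unknown onset, and that they disappear from every AE table and listing where nobody could find them. The documents do not support that.

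- The rule states a sufficient condition. It does not say that other records are excluded; it is silent. Omission follows from a literal build, not from a stated exclusion.
- SAP 6.3.2 and 6.4.1 promise that all data will be listed. This leaves the listing outcome unresolved rather than settled. It is not a rescue, though: section 9 names no listing that would hold a non-TEAE, and sections 7.2, 7.4, 7.5 and 8.2 to 8.5 already withhold listings of other data.
- SAP 6.3.6 maps observed data to SDTM, so the record survives in the datasets.
- Serious events are largely covered by the start-date requirement in protocol 9.5.
- The trigger is narrow. Not even the year of onset may be known, yet visits are every 12 weeks and protocol 9.1 has investigators ask about events since the last assessment. Some events could also qualify through dated worsening.
- Protocol 9.1 starts AE monitoring at dosing, which should limit pre-dose records. The Day 1 carry-over from the parent study means that it does not rule them out.
- The SAP is abbreviated and descriptive, for a programme that is closing.

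These points limit the size and certainty of the first problem. They do not supply the missing rule. They also leave the second problem largely untouched, because there the rule is explicit and yields an impossible date order.

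**Conclusion.** Both defects hold, with different standing. The ongoing event with no start date is an omission in the plan: its status is undefined, and a literal program would drop it from the treatment-emergent outputs, mainly for non-serious events. The start-after-stop result follows directly from the stated partial-date rules and creates false TEAEs.

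The net direction is unknown, because the first lowers counts and the second raises them. The size is also unknown, because the documents give no number of affected records. The 0.56 to 2.8 point range rests on an assumed 1 to 5 subjects among 180. It also requires those subjects to fall in the same row with no other qualifying event there, since SAP 8.1 counts a subject once per preferred term. With fewer than 180 subjects, each one would weigh more. It is worth correcting before lock because the AE outputs carry the whole safety report and the repair is small.

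**What to change.** Replace the sentence on wholly missing start dates in SAP 6.3.2 with: 'An AE with a completely missing start date is a TEAE unless its recorded or imputed end date is before the first OLE dose; an ongoing AE is a TEAE.'

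Add after the partial-date bullets: 'An imputed start date may not be later than a recorded end date; an AE whose recorded end date precedes first OLE dose is not a TEAE.'

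Then reconcile the all-data statements in 6.3.2 and 6.4.1 with the TEAE-only listings in section 9. One way is to let Listing 16.2.7.1 carry all AEs with a TEAE flag; narrowing the two statements would also remove the contradiction, though it would leave non-TEAEs unlisted.

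The cost is two sentences and, if the listing is widened, one program filter, all before database lock. The downside is that a few long-standing conditions of unknown onset may be counted as treatment-emergent. That errs in the same cautious direction as the SAP's defaults for missing severity and relationship.

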## 6.3.2.1. Imputation Methods

Observed cases, without imputation, will be used for the analyses.

If the relationship of an AE is missing, it will be considered treatment-related. Missing AE severity will be coded as severe.

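### SAP 6.3.2: an AE start date with the month missing can be sent to January of the first-dose year, before first OLE dose, although the event may have begun after it

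*SAP*

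**What the plan says.** SAP 6.3.2 gives three rules for partly missing AE start dates and one for a wholly missing start.

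- **Month missing, day and year known.** The start takes the first-dose "month if AE start day greater than or equal to first dose day and if the year is the same". Failing either condition, it is "otherwise January and impute stop month as last dose date month if AE end day less than". The words after January in that run belong to the stop-date rule; the start rule makes no use of the AE end date.
- **Only the year known.** "If year is present but month and day are missing, impute start date as first dose date if the year is the same" as that of first dose.
- **Day missing.** "If year and month are present but day is missing, impute start date as first dose day if the" year and month agree with first dose.
- **Whole start date missing.** "If complete Adverse Event (AE) start date is missing and AE end date is on or after the date of first dose", the event counts as a TEAE.

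SAP 6.3.2.1 takes the cautious value for other gaps: "If the relationship of an AE is missing, it will be considered treatment-related. Missing AE severity will be coded as severe". The same subsection also says that analyses use observed cases and no imputation.

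SAP 8.1 restricts AE analyses to TEAEs, where "treatment emergent is defined as any AE with onset or worsening on or after the First Study Dose in the OLE study". The main AE listing in SAP Section 9 is titled "Listing of All TEAEs"; the other three cover TEAEs or serious TEAEs only. SAP 6.3.2 and 6.4.1, however, say that all data will be listed.

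**The concern.** In the first-dose year the January fallback applies only when the AE day is below the first-dose day, so it can only produce a pre-dose date. Knowing more then costs the event its place: a record giving only the year is moved to the first-dose date and kept, while the same record with the day added can be dropped. Both neighbouring partial-date rules, and the defaults for missing relationship and severity, lean the other way.

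A pre-dose default also suits this study poorly. Protocol 9.1 starts AE monitoring at dosing, so OLE records should mostly be post-dose, apart from Day 1 data carried over from the PTI-125-04 Month 24 visit.

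The AE tables carry most of the safety summary. SAP Section 3 drops the descriptive summaries of vital signs, laboratory values and ECGs and relies on significant findings being reported as AEs. A misdated event has little other place to appear.

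**Working it through.** The plan states no figure on this point. The check is an exact calendar enumeration. The documents give no first-dose dates, so 2023 is illustrative.

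**Inputs.** The month-missing start rule (SAP 6.3.2); the TEAE definition (SAP 8.1); visits every 12 weeks (Protocol Section 4); Week 96 = 96 × 7 = 672 days.

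**1. Does January always precede first dose?** Let f be the first-dose date and d the AE day, with d below the day of f and the same year.
- Pairs (f, d) in 2023: 5,373.
- January d on or after f: 0 of 5,373. This includes January first doses, because d is then the lower day of the same month.
- In an earlier year January is rightly pre-dose, and in a later year rightly post-dose. The fault is confined to the first-dose year.

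**2. Could the true onset be post-dose?** Count the pairs in which d is a valid date on or after f in some month of that year.
- Yes: 4,908, and 4,908 / 5,373 = 91.3%, all with a January to November first dose.
- No: 5,373 − 4,908 = 465, all with a December first dose, where the rule is right.
- Leap year 2024: 4,936 of 5,401.

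**3. Example.** First dose 20 January 2023; AE on day 5, month unknown, first reported at Week 12 (20 January + 84 days = 14 April). The possible onsets since dosing are 5 February, 5 March and 5 April. The rule gives 5 January.

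**4. Does the visit interval fix the month?** Usually not. Of the 4,908 pairs, the known day falls in one month of the first 84 days in 438, in two in 1,960 and in three in 2,510. So (1,960 + 2,510) / 4,908 = 91.1% stay ambiguous.

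**5. Size, given that the month is missing.** Assume first-dose dates spread evenly over the year and post-dose onsets uniform in time.
- Same-year onsets from f to 31 December with a lower day: 29,277 / 66,795 = 43.8% pooled, or 40.6% as the mean over first-dose dates.
- All onsets over 672 days: 11.9%, from 21.6% for a first dose in the first quarter to 2.2% in the fourth.
- Month-missing records per expected loss: 1 / 0.1194 = 8.4.

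**6. Outputs.** A non-serious AE leaves tables 14.3.1.1 to 14.3.1.5, which is five. Listing 16.2.7.1 is the sixth output if Section 9 is the full set of listings.

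**7. Does the repair need the end date?** Take first dose 20 March, start day 5, end 25 March. The possible onsets are 5 January, 5 February and 5 March, all pre-dose. Moving the start to the first post-dose fifth gives 5 April, after the event ended. The gap from first dose to the first feasible post-dose date averages 20 days over the 4,908 pairs (range 1 to 58), so the repair must respect the end date.

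**The case against.** **The no-imputation sentence in SAP 6.3.2.1 may override the date rules.** If so, January is never imputed. The rules in 6.3.2 are written for AE dates specifically and say that they impute, so they are the better reading. The two subsections still conflict, and the consequence described here depends on 6.3.2 governing. This stands as a condition.

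**All data are to be listed.** A reader might infer that the event vanishes from every output. The documents do not support that: SAP 6.3.2 and 6.4.1 promise listings of all data, while Section 9 names only TEAE and serious-TEAE listings. Loss from the tables follows from SAP 8.1; loss from the listings is unresolved.

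**The end-date rule may rescue the event.** If a missing complete start date is meant to include partial dates, AEs ending on or after first dose are kept. That is not the natural reading, since partial dates have their own rules, and AEs with no end date would still be lost. If 10% to 50% of records had no end date (an assumption), the 11.9% would fall to 0.119 × 0.10 = 1.2% up to 0.119 × 0.50 = 6.0%.

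**The pattern is rare.** This stands. A known day and year with an unknown month is unusual, Protocol 9.1 requires full AE documentation, and Protocol 9.5 requires a start date in the 24-hour SAE report. The outputs are single-arm counts without inference.

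**Conclusion.** The January fallback is wrong for January to November first doses and right for December ones. If SAP 6.3.2 governs AE dates, an event that may have begun after first OLE dose loses TEAE status unless worsening is recorded, and an ordinary non-serious event leaves five tables.

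This is a minor correction to a descriptive safety summary. A reader might take the 91.3% as the share of AEs lost, or infer a material undercount. Neither follows: it is a share of calendar pairs, the 11.9% is conditional on a missing month and on uniform onsets, and the documents do not say how many such records exist. Nor does the error separate exposed from unexposed time. PTI-125-04 ended with 6 months of open-label simufilam (Protocol 2.3), so an event shortly before Day 1 may also have occurred on drug. What is misassigned is the study to which the event belongs.

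**What to change.** In SAP 6.3.2, for a start in the first-dose year with the month missing, impute the earliest month in which the known day is a valid date on or after first dose and not after the AE end date. For this test take a partial end date at its latest possible value, and set no upper limit where there is no end date. If no such month exists, the event stays pre-dose. Leave the worsening clause in SAP 8.1 unchanged.

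State in SAP 6.3.2.1 that the no-imputation sentence does not apply to AE dates. It would also help to say whether AEs classed as not treatment-emergent will be listed.

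The cost is a few sentences and one derivation line, with no new data. SAP 2.1 places approval before database lock; after approval, SAP 2.2 provides a Note to File for material deviations.

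The downside is that some AEs that began before first OLE dose, including on open-label simufilam in PTI-125-04, may be tabulated as OLE TEAEs. If onsets were uniform over the whole first-dose year, about 50% of the affected January to November records would be pre-dose, before the end-date test removes any. That assumption ignores that AE monitoring starts at dosing, so it probably overstates the share.
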